12.1 General Considerations

Continuous measures will be summarized with sample size, mean, median, standard deviation, minimum and maximum; categorical measures will be presented with the counts and percentages of subjects in each category.

The date of enrollment will be considered study day 1.

12.2 Analysis Populations

The primary endpoint will be analyzed among all subjects with an overall score reported on the OHIP questionnaire for both the Cobalt Chrome and Polymer Frame.

12.3 Subject Disposition

Subject disposition will be presented by:

- Summary of completed subjects per follow up.
- Summary of discontinuation in the study and reason for discontinuation.

12.4 Demographics and Baseline Characteristics

Demographics and baseline characteristics of enrolled subjects will be summarized. These factors will include (but not be limited to):

- Age
- Gender
- Race and Ethnicity

12.5 Primary Analysis

12.5.1 Primary Objective

The purpose of the study is to evaluate the change in patient Oral Health-related Quality of Life (OHRQoL) from wearing a cobalt chrome (CoCr) removable partial denture (RPD) to wearing the Solvay Dental 360TM polymer Removable Partial Denture (RPD) for 8 weeks.

12.5.1.1 Endpoint Definition

The primary endpoint in this study is the change in patient oral health related quality of life (OHRQoL) after wearing the polymer removable partial denture (RPD) and cobalt chrome (CoCr) removable partial denture (RPD).

12.5.1.2 Hypothesis and/or parameters to be estimated

The primary endpoint analysis will be performed on all subjects with an overall score reported on the OHIP questionnaire for both the Cobalt Chrome and Polymer Frame. The objective of the primary analysis is to show non-inferiority of the difference in the overall score of the OHIP questionnaire after using the CoCr removable partial denture and after using the polymer RPD to a performance goal of 1.5. The hypothesis will be tested, and can be written as follows:

$H_0: OS_{diff} > \Delta$ versus

$H_A: OS_{diff} \leq \Delta$,

where

- OS_{diff} is the overall score for the cobalt chrome frame subtracted from the overall score for the polymer frame
- Δ is the performance goal

The statistical analysis of the non-inferiority of the difference in the overall score from the OHIP for each frame to a performance goal of 1.5 will be done using the PROC TTEST procedure in SAS.

12.5.1.3 Data Collection and Analysis Methods

Results of the OHIP questionnaire for the metal and polymer frame are collected on the OHIP CRF at the corresponding visit (Visit 2 and Visit 8). The overall score for each frame is calculated by a summation of the score from each of the 14 questions; each having the following scoring:

Response	Score
Never	0 Points
Hardly Ever	1 Point
Occasionally	2 Points
Fairly Often	3 Points
Very Often	4 Points

Thus the range of possible scores for the overall score is 0 to 56. Questions that are left blank or responded to with a 'Don't Know' response will be recoded as the average score of all available responses for the subject at the corresponding time point.

The overall score from the questionnaire provided at baseline to assess the cobalt chrome frame will be subtracted from the overall score obtained at 8 weeks follow-up when assessing the polymer frame.

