### 12.1.2. Study Cohorts for Analyses

Because this is a prospective observational study, all subjects with available questionnaire data at both baseline and follow-up will be included in the study cohort for analysis.

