### 12.1.6. Missing Data

It is anticipated that missing data will be very minimal. Every effort will be made to collect complete data from all patients. In the event of missing data, the extent and types of missing data will be assessed and reported.

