## 12.2. Sample Size Determination

In a previous study (S. Shaghaghian, 2014), the average overall score on the OHIP questionnaire for subjects wearing a cobalt chrome denture was 13.8 (standard deviation = 10.1). Based on the anticipated improved performance of the polymer frame, 36 subjects with an alpha level of 0.05 provides approximately 80% power to detect a difference of -3 (standard deviation = 11) between the 2 overall scores with a non-inferiority margin of 1.5. The total number of subjects enrolled will be 40, given the anticipated attrition rate of 10%.

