11.1 Data Handling and Transfer

Data management will be undertaken by NAMSA. NAMSA Biostatistics will be provided access to download SAS datasets or will be provided them upon request.

Programming of analysis datasets, tables, figures and listings will be conducted during the data management phase of the study. Tables, figures, and listings may be reviewed prior to final data lock for data review. Any data values requiring investigation or correction will be identified, and protocol deviations will be reviewed. The final run of outputs will take place after the data is deemed final.

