11.2 Missing Data

Endpoint data may be missing because patients have died, refused follow-up, or have withdrawn from the study. The missing data does not bias the results as long as the data is missing at random. The primary analysis will be done on all patients who have an overall score from the baseline and 8 week OHIP questionnaire.

All efforts will be made to obtain information regarding subject's overall score on the OHIP questionnaire. The sponsor will report the reason for censoring for all subjects with missing endpoint data.

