12.7 Exploratory Analyses

Additional analyses may be performed but are not currently planned or part of the primary and secondary endpoints of the study.

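### Does filling in unanswered OHIP-14 items from the subject's own average, with no minimum number answered, put the primary result at risk?

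*SAP*

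**What the plan says.** SAP 12.5.1.3 sums 14 items scored 0 to 4, giving a total of 0 to 56. An item left blank or answered Don't Know "will be recoded as the average score of all available responses for the subject at the corresponding time point". The week-8 total minus the baseline total is then tested against 1.5.

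The analysis set follows from that total. SAP 12.2 takes "all subjects with an overall score reported on the OHIP questionnaire for both the Cobalt Chrome and Polymer Frame", and SAP 11.2 says the same: "The primary analysis will be done on all patients who have an overall score from the baseline and 8 week OHIP questionnaire". Protocol 12.1.2 is looser: "all subjects with available questionnaire data at both baseline and follow-up will be included in the study cohort for analysis". None of these sections sets a minimum number of answered items.

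On reporting, Protocol 12.1.6 expects little missing data and undertakes that, where it occurs, "the extent and types of missing data will be assessed and reported". Protocol 11 provides for data queries to the sites. SAP 12.7 states: "Additional analyses may be performed but are not currently planned".

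**The concern.** Read literally, the rule lets one answered item stand for all 14. Such a form can score only 0, 14, 28, 42 or 56, and it still enters the primary analysis. Because the average is taken separately at each visit, the baseline and week-8 totals can also rest on different items. If subjects skipped items that tend to score high, and did so only at week 8, the polymer total would come out too low and the comparison would tilt towards non-inferiority.

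The margin is only 1.5 points on a 56-point scale, so a modest tilt might seem to matter. No planned analysis tests for it. The study is unblinded (SAP 9.2), and SAP 11.1 says "Tables, figures, and listings may be reviewed prior to final data lock for data review", so a check devised later would carry less weight than one fixed in advance.

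**Working it through.** **Inputs from the documents.** n = 36 evaluable, difference -3, SD of change 11, margin 1.5, alpha 0.05, baseline SD 10.1 (Protocol 12.2, SAP 10); 14 items scored 0-4 (SAP 12.5.1.3). The test is taken as one-sided, since that is what reproduces the stated power.

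**Inputs assumed.** The documents give neither an item-missing rate nor an internal consistency. I use internal consistency a = 0.95 to 0.80, and a gap d of 0.5, 1 or 2 points between skipped and answered items.

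**The plan's own figure.** The protocol says "36 subjects with an alpha level of 0.05 provides approximately 80% power". The noncentrality is (1.5 + 3)/11 × √36 = 2.455. The normal approximation gives Φ(2.455 - 1.645) = 79.1%, in line with the stated figure. The noncentral t gives 77.7%, and 76.6% with 35 subjects.

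**Random omissions: keep or drop one incomplete form?**

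- Residual SD per item = √(10.1² × (1 - a)/14) = 0.604 (a = 0.95) to 1.207 (a = 0.80).
- Error SD of a total with k items answered: e = residual SD × √((14 - k) × 14/k).
- Rise in the variance of the mean if the subject is kept: (e²/36²)/(121/36) = e²/(36 × 121).

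| Items answered | e (points) | Rise in variance if kept |
|---|---|---|
| 12 | 0.92-1.84 | 0.02-0.08% |
| 10 | 1.43-2.86 | 0.05-0.19% |
| 7 | 2.26-4.52 | 0.12-0.47% |
| 6 | 2.61-5.22 | 0.16-0.62% |
| 4 | 3.57-7.14 | 0.3-1.2% |
| 1 | 8.14-16.29 | 1.5-6.1% |

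- Rise if the subject is dropped: (121/35)/(121/36) - 1 = 2.86%.
- Break-even error: √((121/35 - 121/36) × 36²) = √124.5 = 11.16 points.

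Keeping the form is the better choice at every level shown except possibly a single answered item. A half-form floor would therefore cost precision: at 6 answered it pays only if skipped items differ from answered ones by √(124.5 - e²)/8 = 1.23 to 1.36 points each.

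A separate simulation of 400,000 subjects, calibrated to the plan's figures but with assumed item means and correlations, found bias of at most 0.01 points and type I error at 0.05 under random omission at both visits. Power was 0.773 with complete forms, 0.771 with 2% of items missing, 0.768 with 5% and 0.764 with 10%.

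**Non-random omissions.** The error in a total is -(items skipped) × d, so each imputed item moves the 36-subject mean by d/36.

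| Gap d | Shift per item | Share of margin | Items for 0.15 points | Items for 1.5 points (of 36 × 14 = 504) |
|---|---|---|---|---|
| 0.5 | 0.014 | 0.9% | 11 | 108 (21%) |
| 1 | 0.028 | 1.9% | 6 | 54 (11%) |
| 2 | 0.056 | 3.7% | 3 | 27 (5%) |

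These counts are net: all at one visit and all in one direction.

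**A deliberately adverse case.** Suppose subjects skip the two highest-scoring items at week 8 only. A simulation of 100,000 subjects per setting puts the error at -0.65 to -1.35 points per affected subject. If 4 of 36 do this, the mean shifts by 4/36 of that, -0.07 to -0.15 points, or 5-10% of the margin. Skipping the two lowest-scoring items reverses the sign (+0.57 to +1.07 per affected subject).

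**The case for a change.** The strongest reply is that the rule has no bound, so calling the effect negligible relies on missing data being scarce. That is fair. In the calibrated simulation, power falls from 0.773 to 0.751 with 20% of items missing at random and to 0.688 with 50%. It falls to 0.679 if one form in ten at each visit has a single answer. For one-sided skipping, leaving out the top item at week 8 in 25% of subjects gives bias -0.14 and type I error 0.058; leaving out the top three items in half of subjects gives -0.80 and 0.110. If every subject skipped the one, two or three highest items at week 8 only, the bias would be -0.55, -1.08 or -1.59.

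These figures are right for their scenarios, but nothing in the documents points to such patterns. Protocol 12.1.6 expects the opposite, and no direction of skipping is indicated.

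A second reply is that the promised missing-data report might leave out Don't Know answers, and that nobody has undertaken to count imputed items by visit. This stands as a reporting detail. A count, or a supplementary analysis of items answered at both visits, would show whether imputation mattered. Neither would change the primary result, and Protocol 12.3 leaves room for additional analyses. The common-items analysis also has costs: under two random omissions its scoring error is slightly larger (SD 1.1-1.4 against 0.9-1.2), and it requires skipped and answered items to change alike.

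The unblinding argument carries little weight against the primary analysis. The rule is mechanical and already written down, so an early look at tables leaves no scoring choice open. The loose wording of Protocol 12.1.2 is settled by SAP 12.2 and 12.5.1.3 together. A wholly blank form has no answers to average, so it yields no total and the subject drops out.

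**Conclusion.** The concern does not hold. The SAP has a complete, prespecified rule for unanswered items, and following it gives a sound primary analysis. Random omission causes no bias, costs about one point of power or less up to 10% of items missing, and is cheaper than excluding the subject (0.05-0.19% against 2.9% in variance for a form with 10 answered). The adverse case of 4 subjects in 36 moves the mean by at most 0.15 points against a margin of 1.5, and the sign depends on which items are skipped.

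The conclusion rests on the protocol's expectation of little missing data and on the assumed internal consistency, item gaps and item structure; it would not carry over to heavy item loss concentrated at one visit. The sample size, alpha and margin are unaffected. The absence of a minimum is missing detail at the extreme, and the usual half-form floor would be a convention that, under random omission, loses more precision than it saves.

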12.6 Secondary Analysis

All secondary endpoints will be assessed for all subjects with available data. No formal statistical hypothesis testing will be performed. All objectives will be summarized descriptively as described in section 12.1.

12.6.1 Secondary Objective #1

The first secondary objective of the study is to investigate the difference in health of the abutment teeth following the use of the polymer RPD as compared to the CoCr RPD as assessed by the plaque score and gingival bleeding index.

12.6.1.1 Endpoint Definition

The first secondary endpoint is the health of the abutment teeth during/following the use of the polymer RPD as compared to the CoCr RPD.

12.6.1.2 Hypothesis and/or parameters to be estimated

No formal statistical hypothesis testing will be performed for the secondary endpoint, however, the arch plaque score and bleeding on probing will be summarized as a continuous variable at Visit 2 (corresponding to the metal frame) and Visit 8 (corresponding to the polymer frame). The gingival bleeding index of abutment teeth as compared to baseline will only be summarized at Visit 8, with frequencies of improved, worsened, or no change.

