12.6.2 Secondary Objective #2

The second secondary objective of the study is to investigate the difference in whole plaque score following the use of the polymer RPD as compared to the CoCr RPD.

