12.6.2.2 Hypothesis and/or parameters to be estimated

No formal statistical hypothesis testing will be performed for the secondary endpoint, however, the whole plaque score will be summarized as continuous variable at Visit 2 (corresponding to the metal frame) and Visit 8 (corresponding to the polymer frame).

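### Secondary Objectives 1 and 2 ask for a difference between dentures, but plaque and bleeding on probing are only summarised visit by visit, with no within-subject change or interval

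*SAP*

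**What the plan says.** SAP 12.6.1 sets Objective 1 as to "investigate the difference in health of the abutment teeth following the use of the polymer RPD" against the cobalt chrome denture, assessed by plaque score and gingival bleeding index. SAP 12.6.2 sets Objective 2 as to "investigate the difference in whole plaque score following the use of the polymer RPD as compared to the CoCr RPD".

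The planned outputs are:

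- **Arch plaque and bleeding on probing (SAP 12.6.1.2):** "the arch plaque score and bleeding on probing will be summarized as a continuous variable at Visit 2 (corresponding to the metal frame"), with a second such summary at Visit 8 for the polymer frame. Objective 1 does not itself name bleeding on probing, but the SAP reports it there.
- **Whole plaque (SAP 12.6.2.2):** "the whole plaque score will be summarized as continuous variable at Visit 2 (corresponding to the metal frame) and Visit 8".
- **Analysis set (SAP 12.6):** "All secondary endpoints will be assessed for all subjects with available data".
- **Statistics (SAP 12.6):** "All objectives will be summarized descriptively as described in section 12.1". Section 12.1 reads: "Continuous measures will be summarized with sample size, mean, median, standard deviation, minimum and maximum".

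The protocol adds nothing further for these measures. Its section 12.1.1 defines a change score for the OHIP total only, and section 12.1.4 says that plaque is summarised at baseline and at follow-up.

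**The concern.** Every subject is measured with both dentures and serves as their own control. The mean within-subject change is therefore the direct estimate of the difference that Objectives 1 and 2 name. The SAP already works this way for the primary endpoint: in 12.5.1.3 the baseline OHIP score "will be subtracted from the overall score obtained at 8 weeks follow-up when assessing the polymer frame". For plaque and bleeding on probing it stops at two side-by-side summaries.

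What is lost is the precision of the difference. Someone reading the final tables would see two means and two SDs. The only interval they could build from these treats the visits as separate samples, and that misstates how well the difference is known.

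**Working it through.** **Is a change or interval planned anywhere?** SAP 12.6.1.2 and 12.6.2.2 give visit summaries only. SAP 12.6.4.2 reports bleeding on probing again, also by visit. The statistics in SAP 12.1 include no change from baseline and no interval. Protocol 12.1.1 lists mean, median, SD and inter-quartile range for continuous variables, again with no interval. So none is planned for arch plaque, bleeding on probing or whole plaque.

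**Number of pairs.** The only sample-size figure in the documents is for the OHIP endpoint (SAP section 10): 36 evaluable subjects, difference -3, SD 11, margin 1.5, alpha 0.05, about 80% power. It reproduces with a one-sided normal approximation:

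- n = [11 × (1.645 + 0.842) / (1.5 + 3)]² = 36.9, against the stated 36. Power at 36 is 79.1%.
- Enrolment: 36 / (1 - 0.10) = 40, as stated.

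This figure is used here only to supply 36 pairs. Nothing in the point depends on the OHIP power.

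**Why two summaries are not enough.** Write s2 and s8 for the SDs at Visits 2 and 8, and r for the within-subject correlation. The variance of the change is s2² + s8² - 2·r·s2·s8. The planned tables supply s2 and s8 but not r.

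**Size.** Take equal SDs at both visits and express half-widths of the 95% interval in units of that SD.

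Independent-samples interval: t(0.975, 70) × √(2/36) = 1.994 × 0.2357 = 0.470.

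Paired interval: t(0.975, 35) × √(2(1 - r)) / √36, with t = 2.030:

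| Assumed r | √(2(1 - r)) | Paired half-width | Independent / paired |
|---|---|---|---|
| 0 | 1.414 | 0.479 | 0.98 |
| 0.2 | 1.265 | 0.428 | 1.10 |
| 0.5 | 1.000 | 0.338 | 1.39 |
| 0.8 | 0.632 | 0.214 | 2.20 |

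The documents give neither the correlation nor an SD for plaque or bleeding on probing, so r is an assumption and the results are in SD units.

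**Are the data there?** SAP 12.6.1.3 lists arch plaque and bleeding on probing on both the Visit 2 and the Visit 8 forms, and SAP 12.6.2.3 does the same for whole plaque. One detail affects the pairing. Protocol 7.3 specifies bleeding on probing at Visit 2 for abutment and adjacent teeth with a six-point assessment, while the Visit 8 list names the measure without teeth or sites.

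**Gingival bleeding index.** Protocol 12.1.4 has it summarised at baseline and follow-up. SAP 12.6.1.2 has it summarised at Visit 8 only, as improved, worsened or unchanged against baseline. SAP 12.6.1.3 lists the index on the Visit 8 form but not on the Visit 2 form.

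**The case against.** The strongest reply is that the SAP deliberately keeps the secondary endpoints descriptive. Sections 7 and 12.6 rule out formal testing, the objectives say only that a difference is to be investigated, and side-by-side means show its direction and size. It is true that the point difference can be read off. But a mean change with an interval is estimation, not a test, so the no-testing rule does not answer the point.

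A second reply is that the gain rests on an assumed correlation. That stands. At r = 0 there is no gain, and at positive r the interval a reader would build errs towards caution. The range shows what may be lost, not what will be.

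Third, Objective 1 names plaque score and gingival bleeding index, and the index already has a planned comparison with baseline. That also stands. The gap concerns plaque, together with bleeding on probing because the SAP reports it under the same objective.

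Three stronger readings are tempting, but the documents do not support them:

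- A reader might infer that the bleeding index has no stated baseline. SAP 12.6.1.2 says the comparison is with baseline, and 12.6.4.2 labels Visit 2 as baseline. What is open is which Visit 2 bleeding value is the comparator, or whether the category is a direct rating made at Visit 8.
- A reader might infer that the available-data rule lets dropout distort the difference materially. Protocol 12.1.6 expects very little missing data, the sample size is reported with each summary, and the documents give no figure that would show a material distortion.
- A reader might infer a serious conflict over the bleeding index. Protocol section 12 describes itself as a summary, and the version history of SAP 2.0 records updates to endpoint data collection and reporting. The Visit 8 rule may be one of these, although the log does not say so. The texts still differ and should be aligned, but this is housekeeping.

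**Conclusion.** The point holds for arch plaque, bleeding on probing and whole plaque: the plan names a difference as the objective and does not provide for estimating it with its precision. On 36 pairs and equal SDs, the interval that can be built from the planned tables is about 1.1, 1.4 or 2.2 times as wide as the paired one at assumed correlations of 0.2, 0.5 and 0.8.

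This is an inexpensive improvement that should be made, not a threat to the trial. The primary analysis, its alpha, the sample size and the success criterion are untouched. A paired interval would also leave the comparison what it is, an unrandomised and unblinded before-after contrast. The bleeding-index mismatch is minor and would not merit a point on its own.

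**What to change.** Keep the visit summaries and add to SAP 12.6.1.2 (arch plaque, bleeding on probing) and 12.6.2.2 (whole plaque):

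> *The within-subject change (Visit 8 minus Visit 2) will be summarised with the statistics of section 12.1 and a 95% CI for the mean change, in subjects with values at both visits; no hypothesis test will be performed.*

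Two details belong with it:

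- If a measure is recorded per tooth or per site, reduce it to one value per subject first.
- Compute the change in bleeding on probing on the same teeth and sites at both visits, and state this, because the protocol's Visit 8 list does not.

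As housekeeping, align protocol 12.1.4 with SAP 12.6.1.2 on when the gingival bleeding index is summarised. State which Visit 2 bleeding value is the comparator, or that the category is a direct Visit 8 rating.

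The cost is one sentence in each of two SAP sections, a few table rows from variables already collected at both visits, and a short matching edit for the bleeding index. No new assessments or visits are needed, and the sample size does not change.
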